6.4. PROTOCOL DEVIATIONS

All protocol deviations related to study inclusion or exclusion criteria, conduct of the trial, subject management or subject assessment will be listed. Protocol deviations will be reviewed by the Sponsor, the principal investigator, the lead statistician and the study scientist and will be finalized before unblinding the study. All deviations will be listed.

7. GENERAL ASPECTS FOR STATISTICAL ANALYSIS

7.1. GENERAL METHODS

Study data will be reported in subject data listings and summary tables. Descriptive statistics will be provided by cohort or treatment group and observation time (visit) of interest, as appropriate. If not specified otherwise, the standard summary statistics that will be calculated for quantitative and qualitative variables are:

Continuous: number of subjects (N), mean, SD or standard error (SE), minimum, median, and maximum

Categorical: number of subjects, absolute and relative frequencies per class (denominators for relative frequencies will be described in the tables)

Frequency counts of 0 will be reported as "0" with no percentage.

Data collected pre- and post-treatment during the Dose Selection Phase will be summarized by time point and cohort (PD [i.e., pupillometry], PK plasma concentrations) or as maximum, minimum and final post-dose individual values by cohort (vital signs).

Data collected at other "off-treatment" times (e.g., baseline, admission and follow-up) will be summarized by cohort. These data include demography, baseline conditions, and safety evaluations (lab, ECG).

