3.5. TREATMENT ASSIGNMENT & BLINDING

Randomization will be used to avoid bias in the assignment of subjects to treatment sequences, to increase the likelihood that known and unknown subject attributes (e.g., demographics and baseline characteristics) are evenly balanced across treatment groups, and to enhance the validity of statistical comparisons across treatment groups.

Each potential subject will be assigned a unique number in the screening process (subject number). This number will be used to identify the subject throughout the study. Subjects who enter the Treatment Phase will be assigned a unique randomization number to identify their sequence of study treatments. Once any subject number is assigned, it cannot be reassigned to any other subject.

All randomization codes will be generated by the designated unblinded statistician(s) at Syneos Health before the start of the study. Sealed code break envelopes will be provided before the start of the study.

Each subject will participate in a naloxone challenge, by which subjects will receive 0.2 mg of naloxone via an IV bolus followed by 0.6 mg naloxone IV if no withdrawal signs are observed. At least 12 hours after the naloxone challenge, eligible subjects will be randomized to either placebo or active treatment (allocation 6 Active: 2 Placebo) in a double-blind manner according to the randomization schedule. For each dose selection cohort, an unblinded statistician from Syneos Health, not otherwise involved in the study, will prepare a list of subject randomization numbers. These randomization numbers will be used to prepare individual subject doses. Sealed dose selection code break envelopes will be available for each subject in case of emergency. Upon completion of each cohort of subjects, the randomization codes for the completed

subjects will be unblinded, and the PD and safety data will be reviewed to determine if dose escalation to the next cohort should occur.

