8. DEMOGRAPHIC, OTHER BASELINE CHARACTERISTICS AND MEDICATION

8.1. SUBJECT DISPOSITION AND WITHDRAWALS

Subject disposition will be summarized by treatment. The number of subjects in each cohort will be presented, in addition to the number of subjects who completed, the number of subjects who discontinued the study early along with the reasons for all post-randomization discontinuations.

The number and percentage of subjects in the analysis populations will be presented in the subject disposition tables.

The denominators for the percent calculations will be the number of subjects randomized.

A listing of subjects who participated in the study will also be presented, including participation (yes/no) and treatment received.

Listings of subjects excluded from the analysis sets will also be produced.

Inclusion/exclusion criteria definitions and all deviations will be listed. If no inclusion/exclusion criteria are reported, this will be noted in place of the listing.

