8.2. DEMOGRAPHIC AND OTHER BASELINE CHARACTERISTICS

Demographics and baseline characteristics (age, sex, race, ethnicity, body weight, height, and BMI) will be summarized using descriptive statistics (n, mean, SD, minimum, median and maximum, for continuous variables, and the proportion of subjects for categorical variables). Summaries will be presented by treatment for the Dose Selection Randomized Population. No formal statistical comparison between the groups will be performed.

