13.2.4. Column Headers

- Column headings will be displayed immediately below the solid line described above in initial upper-case characters.
- In the case of PD tables, the variable (or characteristic) column will be on the far left followed by the treatment group columns and total column (if applicable). P-values will be presented under the total column or in separate P-value column (if applicable). Within-treatment comparisons may have P-values presented in a row beneath the summary statistics for that treatment.
- For numeric variables, include “unit” in column or row heading when appropriate.
- Analysis population sizes will be presented for each treatment group in the column heading as (N=xx) (or in the row headings if applicable). This is distinct from the ‘n’ used for the descriptive statistics representing the number of subjects in the analysis population.

The order of treatments in the tables and listings will be Placebo first in the case of placebo controlled studies and Active comparators first in the case of active comparator trials, followed by a total column (if applicable).

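### SAP 7.1 groups pupillometry and demography by cohort, against 8.2 and 13.2.4, and the supplied text never says whether placebo is pooled; separately, TA_PAOC is too small when the 24 h reading is missing

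*SAP*

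**What the plan says.** **Grouping.** SAP 7.1 opens by allowing cohort or treatment group, whichever is appropriate. It then becomes specific. Pre- and post-dose data are to be "summarized by time point and cohort (PD [i.e., pupillometry], PK plasma concentrations) or as maximum, minimum and final post-dose individual values by cohort", the last part referring to vital signs. Off-treatment data "will be summarized by cohort. These data include demography, baseline conditions, and safety evaluations (lab, ECG").

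Other sections use a different factor:
- 8.2, demography: "Summaries will be presented by treatment for the Dose Selection Randomized Population".
- 8.1, disposition, uses both words in turn: "Subject disposition will be summarized by treatment. The number of subjects in each cohort will be presented".
- 13.2.4: "In the case of PD tables, the variable (or characteristic) column will be on the far left followed by the treatment group columns", and "The order of treatments in the tables and listings will be Placebo first in the case of placebo controlled studies".
- 11.3 reports adverse events by treatment.
- 11.4 to 11.6 (laboratory, vital signs, ECG) name no cohort, dose or treatment factor.
- 8.5 crosses cohort (glossed as dose level) with treatment (active or placebo), but only for antiemetic use.

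The arms themselves are clear. In 3.5, "eligible subjects will be randomized to either placebo or active treatment (allocation 6 Active: 2 Placebo"), and Table 1 gives one nalbuphine dose (n=6) and placebo (n=2) per cohort. The only pooling statement, in 7.5, concerns centers.

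**TA_PAOC.** SAP 9.1.2 divides the pupillometry area by the time from dosing to 24 h. It computes that area by the linear trapezoid over whichever readings exist, and missing readings are not imputed.

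**The concern.** Demography and pupillometry each have two different instructions. For vital signs, laboratory and ECG, 7.1 is the only specific instruction, and it names a unit that mixes the two arms. Pupillometry and safety are summarised on the Dose Selection Safety Population, which includes placebo subjects, so the word chosen matters there. It does not matter for plasma concentrations, because the PK population holds only nalbuphine recipients.

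What is missing is a rule that turns the arms into table columns. The practical choice is a 2-subject placebo column for each cohort or one pooled placebo column, and that choice decides how usable the placebo reference for pupillometry is. Section 3.5 unblinds each cohort as it finishes, so the rule belongs in the plan and should not be left to programming.

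The TA_PAOC point is a separate derivation error. When the last reading is absent, numerator and divisor cover different intervals.

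**Working it through.** **Inputs.** 6 nalbuphine + 2 placebo = 8 per cohort (SAP 3.2, 3.5, Table 1). The plan has at least 5 cohorts (3.2), and Table 1 lists 7. Placebo subjects therefore total 2 x 5 = 10 or 2 x 7 = 14. Part A has no power calculation to reproduce; 3.4 rests on historical practice.

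**1. What a 2-subject placebo column can show.** The default statistics in 7.1 are "number of subjects (N), mean, SD or standard error (SE), minimum, median, and maximum". With two values the mean equals the median, and the SD is the difference divided by 1.41 (the square root of 2). Mean, SD, minimum, median and maximum together carry two numbers.

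**2. Precision, in units of the between-subject SD (s).** Assumes equal SDs in both arms and no drift between cohorts.
- SE of the placebo mean = 1/sqrt(n).
- SE of nalbuphine minus placebo at one dose = sqrt(1/6 + 1/n).

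| Placebo column | n | SE of mean | SE of difference |
|---|---|---|---|
| Per cohort | 2 | 0.71 | 0.82 |
| Pooled, 5 cohorts | 10 | 0.32 | 0.52 |
| Pooled, 7 cohorts | 14 | 0.27 | 0.49 |

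**3. When pooling stops helping.** Let cohort placebo means vary with SD tau, over k cohorts.
- Error variance of the pooled mean, as an estimate of one cohort's placebo mean: s²/(2k) + tau²(k-1)/k.
- Error variance using that cohort's own two subjects: s²/2.
- These are equal when tau² = s²/2, that is tau = 0.71 s, for any k.
- At tau = 0.5 s the pooled error is sqrt(0.10 + 0.20) = 0.55 s for k=5 and sqrt(0.071 + 0.214) = 0.53 s for k=7, against 0.71 s.

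**4. TA_PAOC without the 24 h reading.** The schedule runs pre-dose, 0.25, 0.5, 1, 1.5, 2, 2.5, 3, 4, 5, 6, 8, 10, 12 and 24 h, so the trapezoid stops at 12 h while the stated divisor runs to 24 h. Assumed profile: linear rise to a peak at 0.5 to 1.5 h, then exponential decay.

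Example with peak at 1 h and half-life 4 h, peak effect set to 1: area to 12 h = 5.434, area to 24 h = 6.437. The rule gives 5.434/24 = 0.226 where the full value is 6.437/24 = 0.268, a ratio of 0.844.

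| Assumed effect half-life | Ratio to full value | Understatement |
|---|---|---|
| 2 h | 0.957-0.965 | about 4% |
| 4 h | 0.837-0.851 | 15-16% |
| 6.6 h | 0.736-0.751 | 25-26% |
| 9.6 h | 0.670-0.685 | 32-33% |

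The range 6.6 to 9.6 h is the plasma half-life in Protocol 1.1, borrowed here as an effect half-life. The documents give no effect half-life.

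**The case against.** - **7.1 permits either grouping, and the shells may settle it.** This largely stands. The opening sentence of 7.1 defers the choice, and SAP 2.1 counts the table shells as part of the plan. They are a separate attachment that was not supplied, and column layout is what shells fix. The gap is therefore shown only for the supplied text. Even so, 7.1 goes on to name cohort, and text that disagrees with its own shells should be aligned.
- **The conflict is narrow.** This stands. 8.2 speaks only of demography, and the PD-table sentence in 13.2.4 only of PD. A reader might infer a direct contradiction for vital signs, laboratory and ECG as well. The documents do not support that, because 11.4 to 11.6 state no grouping; there it is a gap to align.
- **A reader might infer that the 2 placebo subjects will be averaged with the 6 on nalbuphine, or that all doses will be merged into one active column.** Neither is likely to be intended. 13.2.4 requires columns by treatment group with placebo first, and 8.5 shows that the authors treat cohort as dose level and keep treatment distinct.
- **Little depends on it.** This stands as to severity. No nalbuphine-placebo contrast is planned for pupillometry, and individual data and randomisation codes are listed, so either layout can be rebuilt. A reader might infer an effect on dose escalation, but SAP 2.1 and 5 show Part A was complete when this SAP was written. The SAP is itself inconsistent here: 3.2 says PD data will not be the basis for escalation, while 3.5 says PD and safety data are reviewed for it. Those passages should be reconciled.
- **TA_PAOC could be divided by observed time.** Under the same assumptions, dividing the 12 h area by 12 h overstates the full value by 34-93%, because it leaves out the low late effect. Missing values are reviewed case by case and subjects stay in the unit to about 24 h, so few subjects should be affected; no rate is given.

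**Conclusion.** The concern holds as a minor one. SAP 7.1 conflicts with 8.2 on demography and with 13.2.4 on pupillometry. For vital signs, laboratory and ECG, its by-cohort wording is an unaligned default. Whether placebo is pooled is not stated in the supplied text. Pooling takes the standard error of a dose-placebo difference from 0.82 SD to 0.49-0.52 SD, assuming equal SDs and negligible drift. Pooling remains the better placebo estimate unless drift between cohorts exceeds 0.71 of the between-subject SD.

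The TA_PAOC rule is wrong as written for a subject without the 24 h reading, by about 4-33% under the assumed profile and half-lives. Neither point touches an error rate or power: Part A is descriptive, and adverse events are already by treatment. Confidence is medium, mainly because the shells were not seen.

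**What to change.** 1. In SAP 7.1, for data that include placebo subjects, replace the by-cohort grouping with: nalbuphine by dose level, plus one placebo group pooled across cohorts. Align 8.2, 11.3 to 11.6 and the shells with that definition, and check that 13.2.4 agrees.
2. Use the existing individual listings to look at placebo by cohort for drift, since pooling assumes there is little.
3. In 9.1.2, set TA_PAOC to missing when the 24 h reading is missing.

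Cost: a few sentences and a check of the shells, with no new data. The third change loses a value only for subjects without that reading.

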7.2. KEY DEFINITIONS

Administration of the first dose of study drug during the Dose Selection Phase is defined as Study Day 1. Study Day -1 is the day before dosing and all assessments prior to Study Day 1, including Screening will have negative study days. Nominal Time is the scheduled measurement time relative to time 0. Time 0 is the time of dosing on Day 1. Time 0 is precisely defined for each analysis below. For data collected pre- and post-administration, baseline is the last observed measurement prior to the administration of study drug. Hence, we have one possible baseline.

For AEs and concomitant medications (CMs), time since dose will be calculated as the difference between the event or medication start date/time and the date/time of the treatment dose of each period. Time since dose will be expressed in days, hours and minutes. If onset time is in seconds, it will be expressed as "<1 min". If time is missing, duration will be expressed in days. Methods for handling partial start date/times of AEs and CMs are described in Section 7.3.

Duration will be calculated for AEs that resolve as the difference between the resolution date/time and onset date/time and will be expressed in days, hours and minutes. If duration is in seconds, it will be expressed as "<1 min". If time is missing, duration will be expressed in days. Methods for handling partial resolution and onset dates of AEs and CMs onset are described in Section 7.3.

Age is calculated based on the date of birth and date of full informed consent on the database level and this value will be used in analyses. In case date of birth was provided as year only, age is calculated as difference of 01Jan<year of birth> and date of informed consent.

A subject will be defined as “completed” if s/he completes the Follow-up Visit 10. Termination at a different time point will be considered as discontinuation. This applies only for the Treatment Phase.

Subjects will be defined as “completed” if s/he completes Visit 2. Termination at a different time point will be considered as discontinuation.

Nominal Time is the scheduled measurement time of the time point relative to the dose time.

Time since dose is the actual elapsed time from the first administration of study drug in a cohort. So, for example, if study drug is administered at 08:00 on Day 1, 10:30 on Day 1 represents a Time Since Dose of 2:30 or 2.5 hours.

7.3. MISSING DATA

For PD and PK analyses, missing data for subjects who are administered all scheduled study treatments for all the treatment periods will be considered as random non-informative missing for analysis purposes. Missing values will be examined on a case-by-case basis to confirm this. Missing values for PD assessments will not be imputed. The handling of missing PK data is detailed in Section 10.4.

AEs and medications with incomplete start dates and times will be considered as treatment-emergent or prior/concomitant, respectively, according to the following algorithm:

1. If the AE occurrence type is specified for the AE on the eCRF, it will be used to determine treatment-emergence. If the AE occurrence type is ‘Treatment Period X’ then the AE will be assigned as treatment-emergent. This will be verified using the algorithms below (steps 3 through 7).
2. If a medication started and stopped prior to the start of study treatment the medication will be considered prior. This will be verified using the algorithms below (steps 3 through 7).
3. Comments will be reviewed for additional information when treatment emergence is ambiguous.
4. Only the start year is reported: If the year is after or the same as the year of the first dose date, then the event will be considered treatment-emergent.

5. Only the start month and year are reported: If the month/year is after or the same as the month/year of the first dose date, then the event will be considered treatment-emergent.
6. Only the start time is missing: If the event occurred or medication was started on or after the date of the first dose date, then the event will be considered treatment-emergent and the event will be attributed to that treatment; if it occurred before the first dose in the treatment period (e.g., at admission), it will be attributed to the treatment administered in the previous period.
7. For AEs with missing or incomplete start dates, if it can be determined based on the available start date components or the stop date to which treatment group(s) the AE should be assigned to then the AE will be assigned to the appropriate treatment group. If it cannot be determined, then the AE will be assigned to all treatment groups received.

For treatment-emergent AEs (TEAEs), time since dose will be expressed in days, hours and minutes. If either time is missing, time since dose will be expressed in days.

Duration will be calculated for AEs that resolve as the difference between the resolution date and time and onset date and time and will be expressed in days, hours and minutes. If either time is missing, duration will be expressed in days.

Time since dose and duration will only be calculated when both dates are complete.

7.4. VISIT WINDOWS

7.4.1. Pharmacodynamic (PD) Assessments

PK samples will be collected after the completion of all PD assessments within the following allowable windows:

Table 3 Acceptable Collection Window for PD Assessments

Time Point (hours)	Acceptable Collection Window
Pre-dose	Within 2 hours prior to study drug administration
Post-dose time points 0.25h, 0.5h, 1h, 1.5h	±5 minutes of nominal time

7.4.2. Pharmacokinetic (PK) Sample Collection

PK samples will be collected after the completion of all PD assessments within the following allowable windows:

Table 4 Acceptable Collection Window for PK Blood Sample Collection

Time Point (hours)	Acceptable Collection Window
Pre-dose	Within 60 minutes prior to study drug administration
Post-dose time points 0.25h, 0.5h, 1h, 1.5h	Within + 2 minutes of the completion of PD assessments
Post-dose time points 2.0h, 2.5h, 3.0h, 4.0h, 5.0h, 6.0h, 8.0h, 10.0h, 12.0h	Within + 5 minutes of the completion of PD assessments
Post-dose time point 24.0h	Within + 15 minutes of the completion of PD assessments

7.5. POOLING OF CENTERS

This is a single center study, therefore pooling of centers is Not Applicable (NA).

7.6. SUBGROUPS

No subgroups will be evaluated.

8. DEMOGRAPHIC, OTHER BASELINE CHARACTERISTICS AND MEDICATION

8.1. SUBJECT DISPOSITION AND WITHDRAWALS

Subject disposition will be summarized by treatment. The number of subjects in each cohort will be presented, in addition to the number of subjects who completed, the number of subjects who discontinued the study early along with the reasons for all post-randomization discontinuations.

The number and percentage of subjects in the analysis populations will be presented in the subject disposition tables.

The denominators for the percent calculations will be the number of subjects randomized.

A listing of subjects who participated in the study will also be presented, including participation (yes/no) and treatment received.

Listings of subjects excluded from the analysis sets will also be produced.

Inclusion/exclusion criteria definitions and all deviations will be listed. If no inclusion/exclusion criteria are reported, this will be noted in place of the listing.

8.2. DEMOGRAPHIC AND OTHER BASELINE CHARACTERISTICS

Demographics and baseline characteristics (age, sex, race, ethnicity, body weight, height, and BMI) will be summarized using descriptive statistics (n, mean, SD, minimum, median and maximum, for continuous variables, and the proportion of subjects for categorical variables). Summaries will be presented by treatment for the Dose Selection Randomized Population. No formal statistical comparison between the groups will be performed.

8.3. OTHER BASELINE CHARACTERISTICS

8.3.1. Recreational Drug and Alcohol Use History

A history of all drugs used for recreational/non-medicinal purposes (i.e., psychoactive effects) and alcohol use will be collected during the Screening visit(s) and listed by subject for Dose Selection Randomized Population.

The number and percent of subjects with history in each drug class (cannabinoids, depressants, dissociative anesthetics, hallucinogens, opioids and morphine derivatives, stimulants and other compounds) will be presented by treatment for the Dose Selection Randomized Population. For each drug class, the proportion of subjects with a history of the given drug class are summarized.

For all recreational drugs, the following questions will be tabulated using standard summary statistics:

- Number of times used in past 2 years
- Number of recreational drugs used in past 2 years (1, 2, 3 or ≥ 4)

For the opioids drug class, the following two additional questions will be tabulated using standard summary statistics:

- Number of times opioids used in the past 8 weeks prior to Screening visit
- Number of times opioids used in the past 12 months

For subjects reporting more than one drug per drug class, number of times used will be summed over all drugs in that class.

The number and percentage of subjects reporting drinking alcohol will be presented by treatment for the Dose Selection Randomized Population. The average number of drinks in the past 2 years will be tabulated using standard summary statistics.

